3.2.2 Clinical Safety Laboratories

The evaluation of clinical safety laboratories, including blood hematology, chemistry, coagulation, and urinalysis, will be based on the observed values. Observed values and changes from baseline will be summarized for all post-baseline study visits.

3.2.3 ECG, Vital Signs and PE

The evaluation of ECG and vital signs (including heart rate, systolic blood pressure, diastolic blood pressure, weight, height [baseline only], and body mass index [BMI]), will be based on the observed values. For ECGs, shifts from baseline to end-of-study will be summarized. For vital signs, observed values and changes from baseline will be summarized for all post-baseline study visits. Listings of PE data will include only those records where the body system at the baseline PE was normal, but the body system at a post-baseline PE was marked as 'Change from previous exam, clinically significant.'

3.3 Primary Efficacy Endpoints

3.3.1 Primary Efficacy Endpoint

Percent change from baseline to Week 12 in LDL-C

3.3.2 Key Secondary Efficacy Endpoints

- 1) percent change from baseline to Week 24 in LDL-C
- 2) percent change from baseline to Week 12 in non-HDL-C
- 3) percent change from baseline to Week 12 in TC
- 4) percent change from baseline to Week 12 in apoB
- 5) percent change from baseline to Week 12 in hsCRP

3.3.3 Other Efficacy Endpoints

Percent change or change in LDL-C, HDL-C, TGs, TC, non-HDL-C, hsCRP, and apoB values at other protocol-scheduled time points will also be evaluated as secondary efficacy endpoints (See Section 5.3 for more information)

Proportion of patients achieving LDL-C < 70 mg/dL at week 12, 24 and 52 will be evaluated.

3.4 Pharmacokinetic (PK) and Other Biomarkers

Trough plasma concentrations will be collected at Weeks 12, 24, and 52 from patients randomized into the study prior to the implementation of Protocol Amendment 3 for use in further developing the population pharmacokinetic (PK) model. Trough plasma

concentrations will not be collected from patients randomized into the study after the implementation of Protocol Amendment 3 in the EU, Protocol Amendment 4 in the US. PK analysis will be based on PK concentration population using the actual treatment received.

[figure not shown]
4 Study Design

4.1 Study Design

This is a Phase 3, randomized, double-blind, placebo-controlled, parallel group study evaluating the long-term safety and tolerability of ETC-1002 in high cardiovascular (CV) risk patients with hyperlipidemia (patients with underlying HeFH and/or ASCVD) who are not adequately treated with their maximally tolerated lipid-modifying therapy. Maximally tolerated lipid-lowering therapy includes a maximally tolerated statin alone or in combination with other lipid-lowering therapies, in patients with hyperlipidemia. A patient's maximally tolerated lipid-modifying therapy will be determined by the investigator using their medical judgment and available sources, including the patient's self-reported history of lipid-modifying therapy.

The study will be conducted at approximately 125 clinical sites in the United States, Canada, Germany, Netherlands, Poland, and United Kingdom. The study will end when the last randomized patient completes their last study visit (last patient last visit [LPLV] for last randomized patient). The estimated overall duration of the study (first patient first visit [FPPV] to LPLV) is approximately 28 months.

Figure 1. Study 1002-040 Study Design

4.2 Study Treatments and Assessments

Screening (Visit S1) will occur approximately 2 weeks prior to Day 1 (Visit T1). Patients on maximally tolerated lipid-lowering therapy, as determined by the investigator, will be stratified based on CV risk (HeFH and ASCVD diagnosis) and baseline statin dose category defined in Table 1, where baseline statin dose category is defined in Table 2. There will be no cap placed on randomization into any particular stratum. Patients will be placed in the baseline statin dose category based on their average daily statin dose (some patients do not take a daily statin; for those who do not, their baseline statin category will be based on the average daily statin dose rather than on the actual statin dose).

Table 1: Randomization Strata

HeFH (with or without ASCVD)	ASCVD (without HeFH)
HeFH+ Low Intensity Statins	ASCVD + Low Intensity Statins
HeFH+ Moderate Intensity Statins	ASCVD + Moderate Intensity Statins
HeFH+ High Intensity Statins ^a	ASCVD + High Intensity Statins ^a

ASCVD = Atherosclerotic cardiovascular diseases; HeFH = Heterozygous familial hypercholesterolemia.

^a Simvastatin with doses ≥ 40 mg/day are not allowed in this study.

Table 2: Baseline Statin Dose Categories

High Intensity Statins	Moderate Intensity Statins	Low Intensity Statins^a
Atorvastatin 40-80 mg	Atorvastatin 10-20 mg	Simvastatin 10 mg
Rosuvastatin 20-40 mg	Rosuvastatin 5-10 mg	Pravastatin 10-20 mg
	Simvastatin 20-40 ^b mg	Lovastatin 20 mg
	Pravastatin 40-80 mg	Fluvastatin 20-40 mg
	Lovastatin 40 mg	Pitavastatin 1 mg
	Fluvastatin XL 80 mg	
	Fluvastatin 40 mg BID	
	Pitavastatin 2-4 mg	

^a Low intensity statins also include those patients taking low-dose statins using an alternate regimen (ie, every other day, or for a specified number of times per week)

^b Simvastatin with doses \geq 40 mg/day are not allowed in this study.

The investigational products were listed in Table 3 below:

Table 3: Investigational Medicinal Products

	Investigational Medicinal Product	
Product Name:	ETC-1002	Placebo
Dosage Form:	Film-coated tablets	Film-coated tablets
Unit Dose:	180 mg	Not applicable
Container/Closure^a	35- and/or 100-count bottle (depending upon visit) with screw on, non-child proof cap	35- and/or 100-count bottle (depending upon visit) with screw on, non-child proof cap
Route of Administration:	Oral, daily (once every 24 hours, at approximately the same time each day), with or without food	Oral, daily (once every 24 hours, at approximately the same time each day), with or without food
Physical Description:	Oval, white to off-white film-coated tablet debossed with “ABC” on one face and debossed with “000” on the opposite face	Oval, white to off-white film-coated tablet debossed with “ABC” on one face and debossed with “000” on the opposite face
Manufacturer (Fill/Finish):	Norwich Pharma Services [name] AND: Patheon [name]	Norwich Pharma Services [name] AND: Patheon [name]

^a A 100-day supply of IMP will be included in the 100-count bottle and a 35-day supply of IMP will be included in the 35-count bottle.

Randomized patients will continue in the study until they have completed Week 52 (Visit T7). Randomized patients will return for clinic visits at Week 4 (Visit T2), Week 8 (Visit T3), Week 12 (Visit T4), Week 24 (Visit T5), Week 36 (Visit T6), and Week 52 (Visit T7).

Patients on an average daily dose of simvastatin 40 mg will be scheduled for the additional Visit T4.1 (Week 16) and T5.1 (Week 28) for clinical safety laboratory evaluations specifically to monitor changes in creatine phosphokinase (CPK) and liver function tests (LFTs). On Visit T4.2 (Week 20, phone only), and T5.2 (Week 32, phone only), these patients will be monitored for AE and SAE occurrences.

Patients who withdraw from investigational medicinal product (IMP) treatment will be asked to continue to be followed for safety using the protocol-specified visit schedule and

procedures. For details of study assessments, see Appendix 1: Schedule of Events (Patient Visit Schedule).

An independent expert Data Monitoring Committee (DMC) will formally review accumulating unblinded safety and efficacy data from this and other any ongoing studies of ETC-1002. All clinical cardiovascular endpoints, including all major cardiac events (MACE) and non-MACE endpoints defined as: CV death (MACE), non-CV death (non-MACE), nonfatal myocardial infarction (MI) (MACE), nonfatal stroke (MACE), hospitalization for unstable angina (MACE), coronary revascularization (MACE), non-coronary arterial revascularization (non-MACE), and hospitalization for heart failure (non-MACE), will be adjudicated by an independent blinded expert Clinical Events Committee (CEC), using standardized definitions. Any clinical endpoints that meet serious adverse event (SAE) criteria will be reported as SAEs.

4.3 Randomization and Blinding

For patients who satisfy all entry criteria and complete the 2-week screening period, randomization will occur and their randomization number will be assigned via IWRs at Week 0 (Visit T1). Patients will be stratified on CV risk (HeFH and ASCVD diagnosis) and baseline statin dose and randomized in a ratio of 2:1 to receive 1 of the 2 following treatments in a double-blind fashion:

- ETC-1002 180-mg tablet
- Matching placebo tablet

For details regarding the randomization strata see Table 1.

The randomization code for treatment and IMP packaging will be generated by the Clinical Supply Chain (CSC) department following specifications from the Biostatistics Department. Patients will be randomly assigned to treatment and IMP packing through Interactive Web-based Response System (IWRs). This system is used to ensure a balance across treatment groups within each randomization stratum; no effort will be made to maintain a balance among treatment groups within an investigational center.

4.4 Sample Size Justification

A total of 1950 patients will be enrolled in this study with 1300 patients randomized to ETC 1002 and 650 patients randomized to placebo. Using an anticipated overall dropout rate of 7.5% at 6 months exposure and 10.0% at 12 months exposure in each treatment group, the expected number of patients exposed to treatment during the study is as follows:

	Patients \geq 6 Months	Patients \geq 12 Months
ETC-1002	1,202	1,170
Placebo	601	585

Absolute risk will be addressed by 1300 patients randomized to ETC-1002 and will provide at least 95% power to detect AEs that occur at rates similar to those seen in the placebo group for the AEs of interest in the recently completed long-term safety study entitled Efficacy and Safety of Alirocumab in Reducing Lipids and Cardiovascular Events [5]. In this study, adverse event rates ranged from 0.5% to 13.6%. Additional assumptions include a two-sided test with significance level at 0.05.

When AEs occur at a range of rates similar to those seen in the placebo group in the above referenced alirocumab study (0.5% to 13.6%), the sample size of 1300 patients randomized to ETC 1002 and 650 patients randomized to placebo will allow for detection of relative risks of 1.0 and of 2.0 (ETC-1002: placebo) with the following approximate 95% confidence limits:

% Placebo Patients Experiencing AE	% ETC-1002 Patients Experiencing AE	Relative Risk	Approximate 95% Confidence Interval
0.5%	0.5%	1.0	(0.3, 3.8)
0.5%	1.0%	2.0	(0.6, 6.7)
13.6%	13.6%	1.0	(0.8, 1.3)
13.6%	27.2%	2.0	(1.6, 2.5)

4.5 Interim Analyses, Final Analyses and Unblinding

No interim analysis is planned for this study.

The final analysis will be performed after the database is locked, the treatment assignments are unblinded using the actual randomization, and the database released.

An independent external Data Monitoring Committee (DMC) has been established for this study. Detailed information about the responsibilities and operation of the DMC were provided in the DMC Charter.

4.6 Changes from Protocol Planned Analyses

- 1) Additional subgroup analysis and sensitivity analyses are proposed and described in this SAP.
- 2) It is clarified in the SAP that study objectives are supported by both primary safety and primary efficacy endpoints.
- 3) Multiplicity adjustment amongst efficacy endpoints is implemented and described in this SAP.

5 Statistical and Analytical Plans

5.1 General Statistical Considerations

The ETC-1002 treatment group will be displayed in the tables, listings and figures (TLFs) as “bempedoic acid 180 mg.”

In general, all safety and PK data will be reported as observed. No imputation will be performed for missing data, except for the missing lipid efficacy data (Please refer to Section 5.3.2 for more details). Descriptive statistics (n, mean, standard deviation [SD], Q1, Q3, median, minimum, and maximum) will be calculated for continuous data. Minimum and maximum will be presented same number of decimal places as reported/collected, one additional decimal place for mean and median, and two additional decimal places for SD.

Categorical data will be summarized using n and percentage based on number of non-missing values. Percentage will be presented with one decimal place. The number of missing values will be presented as a separate category with no percentage, but only if 1 or more patients are missing data for the summary. Otherwise, all categories will be presented (even if no patients are counted in the category). Counts of zero in any category will be presented without percentage.

Data will be presented on listings in order of patient, assessment date and assessment (in order collected on CRF, unless specified otherwise). Dates will be presented in format DDMMYY YYYY.

Relative day calculations will be [date of interest – relative date + (date of interest >= relative date)]. This calculation will result in dates prior to the relative date being presented as negative days, and those occurring on or after the relative date as Day 1 or later, i.e., there will be no Day 0.

Baseline for fasting lipid parameters including LDL-C, TC, HDL-C, non-HDL-C, and Triglycerides are defined as the average of S1 and T1 values (last two non-missing values on or prior to Day 1). If only one value is available, the single value will be used as baseline. For other parameters including apoB and hsCRP, the baseline is defined as the last value/result where assessment date is less than or equal to the date of first study treatment, unless otherwise specified. If last dose of study treatment is missing, then the date of last visit at which study assessments were obtained on CRF will be used in its place.

The visit schedules and window are shown below.

Visit	S1	T1	T2	T3	T4	T5	T6	T7, EOS
Slotted Study Week	-2	0	4	8	12	24	36	52
Target Study Day	-16	1	29	57	85	169	253	365
Visit Windows	[-∞, -1]	[1, 1]	[2, 43]	[44, 71]	[72, 127]	[128, 211]	[212, 309]	[310, ∞]
Study Day Range	-16 to -4	1	29±3	57±3	85±3	169±7	253±7	365±7

For Patients on an average daily dose of simvastatin 40 mg, the visit schedules and windows are shown below only for clinical safety laboratory evaluations in creatine phosphokinase (CPK) and LFT related listings and tables.

Visit	S1	T1	T2	T3	T4	T4.1	T4.2	T5	T5.1	T5.2	T6	T7, EOS
Slotted Study Week	-2	0	4	8	12	16	20	24	28	32	36	52
Target Study Day	-16	1	29	57	85	112	140	169	196	224	253	365
Visit Windows	[$-\infty$, -1]	[1, 1]	[2, 43]	[44, 71]	[72, 99]	[100, 127]	[128, 155]	[156, 183]	[184, 211]	[212, 239]	[240, 309]	[310, ∞]
Study Day Range	-16 to -4	1	29 \pm 3	57 \pm 3	85 \pm 3	112 \pm 3	140 \pm 3	169 \pm 7	196 \pm 7	224 \pm 7	253 \pm 7	365 \pm 7

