#### **10.2.8. Treatment Week 52 (Visit T7; ± 7 days)**

Patients will undergo the following assessments and procedures at Week 52 (Visit T7), when completing an End of Study (EOS) visit, withdrawing from study (early withdrawal), or withdrawing from IMP treatment:

Patients will undergo the following assessments and procedures at Week 52 (Visit T7):

- Concomitant and prohibited medication review (ongoing)
- Assess AEs, including muscle-related AEs (ongoing)
- PE
- Weight
- 12-Lead ECG
- Vital signs
- Clinical laboratory evaluations:
  - Hematology, blood chemistry, and urinalysis
  - Basic fasting lipids (TC, calculated LDL-C, HDL-C, non-HDL-C, and TG)
  - apoB
  - HbA1C
  - hs-CRP
  - PK sample (*patients randomized after Protocol Amendment 3 and subsequent amendments are excluded from PK sampling*)
  - Reserve sample
- Return of IMP; assessment and recording of IMP compliance
- Complete study status in IWRS (ie, early withdrawal or completed study)
- *Review and offer the open-label extension study (Study 1002-050) to the patient*

Note: For patients who withdraw from IMP treatment:

- *Capture the reason for withdrawing from IMP treatment and record on the eCRF*
- Determine whether the patient will or will not consent for follow-up visits through study completion
- If the patient provides consent to continue to be followed for safety assessments per the protocol visit schedule, schedule follow-up visits as they would have occurred if the patient were continuing in the study and complete the visit required procedures listed in the appropriate visit specific section within **Section 10** and **Appendix 1**. No further IMP will be dispensed for patients who withdraw from IMP treatment.
- If the patient does not provide consent to be followed for safety assessments per the protocol (either by returning to clinic or by phone), this visit (Visit T7) will be considered the EOS/Early Withdrawal from study visit and no further visits will be scheduled.

Note: If this visit is being conducted at the site for patients who have consented to be followed for safety assessments, *including basic fasting lipids*, after withdrawing from

IMP treatment, all assessments except for those procedures pertaining to apoB, hs-CRP, PK samples, reserve samples, and IMP (IMP dispensing, IMP compliance, IMP accountability) management should be completed.

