## 10.3. Subject Withdrawal Criteria

### 10.3.1. Early Withdrawal from the Study

Patients must remain in the study until the last scheduled visit at Week 52 (Visit T7) to be considered as having completed participation in the study.

Patients who withdraw from IMP prior to Week 52 (Visit T7) for any reason will be asked to continue to be followed for safety assessments, *including basic fasting lipids*, at clinic visit following the protocol-specified visit schedule (see [Appendix 1](#)). The patient must provide consent to be followed in the study after withdrawing from IMP treatment. Protocol procedures to be completed for patients who consent will include those specified at each visit as noted in Schedule of Events (see [Appendix 1](#)).

*Patients who temporarily withdraw from IMP prior to Week 52 (Visit T7) for any reason may restart IMP providing that 1) the patient and the investigator are in agreement regarding this course of action, 2) the patient has been off of IMP for 4 weeks or less; and 3) IMP can be started as soon as possible. For cases where the patient has been off of IMP for more than 4 weeks, the investigator must contact the medical monitor for approval prior to restarting IMP.*

Patients who do not provide consent to continue to return to the clinic for safety assessments will be asked to participate in phone calls from the site at protocol-specified visits (see [Appendix 1](#)), or at a minimum at 52 weeks, to collect information on AEs, *concomitant medications*, and current health status. The patient must provide consent to be contacted by phone by site personnel for the purposes of assessing current AEs and current health status.

The patient's decision to participate in the clinical study is voluntary. Patients may refuse to continue in the study and/or withdraw from participation in this study at any time, for any reason, specified or unspecified, and without penalty or loss of benefits to which the patient is otherwise entitled.

It is the right and duty of the Investigator to interrupt the treatment of any patient whose health or well-being may be threatened by continuation in this study. Such patients should be withdrawn from the study and should not be continued under a modified regimen.

Patients who are withdrawn from the study may not re-enter. The reasons for withdrawal from this study may include:

- Patient's withdrawal of consent
- Failure to comply with the protocol
- Lost to follow-up

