NOTE: For patients who withdraw from IMP treatment, but consent to be followed for safety assessments and return to clinic for these visit, the visits will occur according to the protocol schedule. Safety assessments should include clinical safety and basic lipid laboratories (except for apoB and hs-CRP), adverse events, PE, vital signs, and ECGs. For patients who withdraw from IMP treatment, but consent to be followed for safety assessments by phone, the telephone contacts will occur according the protocol schedule with information regarding current health status and to collect information on AEs (eg, recent procedures, hospitalizations, and if the patient has died, the cause of death). If a patient does not provide consent to be followed for safety assessments per the protocol (either by returning to clinic or by phone), Visit T7 will be considered the EOS/Early Withdrawal from study and no further visits will be scheduled.

 An optional visit approximately 1 week later MAY be completed if patient fails to meet a lipid entry criterion. If this optional visit is completed, the mean of lipid values from both visits will be used to determine eligibility.

 An optional visit between Visits S1 and T1 may be completed if the patient's DBP and/or SBP meet the exclusion criteria levels. Patients may randomize after blood pressure medications have been adjusted, the patients have been on stable doses of blood pressure medications for at least 2 weeks, and the repeat blood pressure values (DBP and/or SBP) do not meet exclusionary values. An optional visit between Visit S1 and T1 may be completed to determine eligibility if the patient's eGFR, ALT, AST, and/or TB meet exclusion criteria levels. If this optional visit is completed, the repeated value will be used to determine eligibility.

 All procedures will be completed for all patients at either End of Study (EOS) if completing the study or early withdrawal.

 Body weight will be measured in the morning while fasting, using consistent scales, after voiding, and without shoes and outerwear (eg, coats).

 Single 12-lead ECG will be collected prior to any blood sample collection.

 Vital signs will include DBP, SBP, and HR and will be collected prior to any blood sample collection. Patient will rest for 5 minutes prior to assessments

 Serology for HBsAg, HCV

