3.2.1 Adverse Events

The evaluation of AEs will include only incidence of treatment-emergent AEs (TEAEs), defined as AEs that begin or worsen after the first dose of IMP until 30 days after last dose of IMP. Clinical endpoints will be collected and adjudicated by an independent

Confidential

Page 7 of 33

Clinical Events Committee (CEC). Clinical endpoints will also be reported as SAEs. Adverse events of special interest (AESI) will further be examined (See Section 5.4.2 for more information).

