5.2.9 IMP Exposure and Compliance

The length of exposure to IMP (ETC-1002 or placebo) will be calculated as the number of days from the first dose of double-blind IMP to the last dose of double-blind IMP, regardless if the patient missed one or more doses of IMP. Length of exposure will be summarized by treatment group using descriptive statistics for the safety population.

The number and percentage of patients who were compliant with taking IMP will be summarized by treatment group for the safety population for the following categories 0- $<80\%$; $\geq 80\%$.

Overall compliance will be calculated as: $100 * (\text{Total Number of Tablets Dispensed} - \text{Total Number of Tablets Returned}) / (\text{Treatment Duration in Days})$. The IMP administration and compliance data, including reasons for poor compliance, if noted in CRF will be listed for each patient.

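### A missing last-dose date is replaced by the last visit with assessments even for patients who stopped IMP and kept attending clinic, so for those few patients off-drug time is counted as treatment.

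*SAP*

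**What the plan says.** The rule is in the baseline paragraph of SAP 5.1: "If last dose of study treatment is missing, then the date of last visit at which study assessments were obtained" is used instead. It is the SAP's only rule for a missing last-dose date, and it carries no condition on treatment status.

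Protocol 10.3.1 states: "Patients who withdraw from IMP prior to Week 52 (Visit T7) for any reason will be asked to continue to be followed for safety assessments". For those who agree, Protocol 10.2.8 tells the site to "schedule follow-up visits as they would have occurred if the patient were continuing in the study". Protocol Appendix 1 lists safety laboratories, basic lipids, adverse events, examinations, vital signs and ECGs for these off-drug clinic visits, but not apoB or hs-CRP. SAP 4.2 repeats the follow-up request.

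The last-dose date is then used in several places:
- SAP 3.2.1 counts as treatment-emergent those events that "begin or worsen after the first dose of IMP until 30 days after last dose of IMP".
- SAP 5.2.9 measures exposure from first to last dose.
- SAP 5.3.4 ends the on-treatment efficacy analysis 7 days after the last dose.
- SAP 5.3.2 treats a patient with missing Week 12 data as off drug when the last dose is more than 7 days before the Week 12 visit.
- SAP 5.2.8 closes the concomitant-medication window 30 days after the last dose.

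**The concern.** The substitute is sound when visits end at about the time dosing ends. This trial deliberately separates the two. An off-drug clinic visit yields assessments, so it qualifies under the rule, and the last such visit may be Week 52.

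The primary objective is long-term safety, and SAP 4.4 presents the sample size through expected numbers exposed for at least 6 and 12 months. A late substituted date moves an early stopper into the 12-month exposure count. It brings off-drug adverse events into the treatment-emergent tables and off-drug lipids into the on-treatment analysis. In the imputation step, a bempedoic acid patient who should be imputed from placebo data would instead be imputed with treatment in the model, which favours the drug if the drug works.

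**Working it through.** **1. The plan's own figures.** SAP 4.4 gives 1300 and 650 patients, with dropout of 7.5% at 6 months and 10.0% at 12 months.
- ETC-1002: 1300 × 0.925 = 1202.5 and 1300 × 0.90 = 1170 (stated 1,202 and 1,170).
- Placebo: 650 × 0.925 = 601.25 and 650 × 0.90 = 585 (stated 601 and 585).

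The planning counts reproduce.

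**2. One affected patient.** Take a patient who stops IMP at a scheduled visit, has no last-dose date and attends to Day 365. Visit days are the SAP 5.1 target days. The substituted date is Day 365 in every row, so the on-treatment cut-off becomes 365 + 7 = Day 372 and the treatment-emergent cut-off 365 + 30 = Day 395.

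| True last dose | Excess exposure (365 − stop) | True on-treatment cut-off (stop + 7) | True treatment-emergent cut-off (stop + 30) | Scheduled lipid visits wrongly kept as on-treatment |
|---|---|---|---|---|
| Day 29 | 336 days | Day 36 | Day 59 | Weeks 8, 12, 24, 36, 52 |
| Day 57 | 308 days | Day 64 | Day 87 | Weeks 12, 24, 36, 52 |
| Day 85 | 280 days | Day 92 | Day 115 | Weeks 24, 36, 52 |
| Day 169 | 196 days | Day 176 | Day 199 | Weeks 36, 52 |
| Day 253 | 112 days | Day 260 | Day 283 | Week 52 |

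**3. How many patients.** Three conditions must hold together: IMP stopped early, last-dose date missing, clinic visits continued. Taking the 10% twelve-month dropout as a proxy for stoppers gives 1950 × 0.10 = 195. The share m of stoppers without a date is not in the documents. Assuming that all of them attend to Week 52:
- m = 0.5%: 195 × 0.005 = 0.98, about 1 patient
- m = 2%: 195 × 0.02 = 3.9, about 4 patients
- m = 10%: 195 × 0.10 = 19.5, about 20 patients

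**4. Effect on totals, ETC-1002 arm.** The 12-month count becomes 1170 + 130m: 1,171 at 0.5%, 1,173 at 2%, 1,183 at 10%.

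For exposure time, assume that stopping is uniform within each half-year (mean stop Day 91.5 for 97.5 patients and Day 274 for 32.5).
- True exposure: (1170 × 365 + 97.5 × 91.5 + 32.5 × 274) / 365.25 = 1218.0 patient-years.
- Maximum excess: (97.5 × 273.5 + 32.5 × 91) / 365.25 = 81.1 patient-years, or 6.7% if every stopper lacked the date.
- Excess at m = 0.5%, 2% and 10%: about 0.03%, 0.13% and 0.67%.

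**5. Imputation split.** With the Week 12 visit at Day 85, off drug means a last dose before Day 78. Assuming linear dropout to 7.5% at Day 182, 0.075 × 78 / 182 = 3.21% are off drug by then, or 41.8 ETC-1002 patients. With the date missing in 2% or 10% of them, 0.8 or 4.2 could be misclassified. An off-drug patient who attends Week 12 has LDL-C, non-HDL-C and TC measured, so those values need no imputation. ApoB and hs-CRP are not drawn, so they are the endpoints mainly exposed.

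**The case against.** The best reply is that the date will seldom be missing. Protocol 10.3.2 requires it at study withdrawal, 16.3 does not allow blank fields, 8.3 requires tablet counts and 9.3 requires dispensing and return records. Patients stopping IMP also complete the 10.2.8 assessments, which include IMP return. This largely stands, and it keeps the point small. It is weakest for the group in question: for patients who stop IMP but remain in follow-up, the 10.2.8 note names only the reason for stopping.

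The rule also gives a reasonable date for patients on drug up to their last visit, and for those who refuse all follow-up, whose withdrawal visit is their last. A full-year patient with a month of tablets would show compliance of about 29/365 = 8% if treatment duration follows the substituted date. That makes the error visible but does not correct it.

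Four stronger readings might be inferred, and the documents do not support them:
- That the rule turns early stoppers in general into full-exposure patients. It applies only where the date is missing.
- That 0.5–2% of all 1950 patients, or 10–39, are harmed. Patients who took drug to their last visit receive roughly the right date.
- That patients followed by telephone also receive a Week 52 date. Follow-up needs consent, and the SAP does not say that a call counts as a visit with assessments.
- That exposure must be reported net of interruptions. SAP 5.2.9 explicitly counts first to last dose "regardless if the patient missed one or more doses of IMP" and deals with missed doses through compliance and listings. A different measure would be a preference.

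**Conclusion.** The point holds, and it is minor. As written, SAP 5.1 gives a wrong last-dose date for a patient who stopped IMP, lacks the date and continues clinic visits. The error for that patient is large: 112 to 336 days in the cases worked, with both windows extended over off-drug time. In aggregate it should be slight, at about 1–4 patients if 0.5–2% of roughly 195 stoppers lack the date and about 20 at 10%. Those shares are assumptions; the 195 uses planned dropout as a proxy for stopping IMP; and full attendance to Week 52 is the unfavourable case. Nothing here suggests that the main safety or LDL-C conclusions would change.

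**What to change.** Replace the sentence in SAP 5.1 with a conditional rule:
- If the last-dose date is missing and IMP discontinuation is recorded, use the earlier of the IMP-withdrawal visit date (when the Protocol 10.2.8 assessments are done) and the final IMP return or accountability date. Taking the earlier date guards against a bottle handed back late.
- If no IMP discontinuation is recorded, use the last visit with assessments, as now.
- Report the number of substituted dates by treatment arm.

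This costs a few lines in the SAP and a small programming change, using records that the protocol already requires. Exposure figures may fall very slightly.
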